### Secondary outcomes

Continuous secondary outcomes will be analysed using the same approach as described for the primary outcome.

We will estimate baseline-adjusted differences between the study groups in change in weight from 4 months to 12 months using a linear regression model with change in weight from 4 months to 12 months as the outcome, and including baseline weight, 4 month weight, the randomisation stratifiers (sex, BMI classification) and intervention group as covariates.

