4.2 Randomisation

Once baseline data have been collected, eligible participants will be allocated to one of the two intervention arms in a 1:1 allocation using block randomisation (block size 6) stratified by BMI classification (25-30, 30-40, 40+) and sex (male, female). The randomisation sequence will be computer-generated by the trial statistician and incorporated into the trial database by the data manager. The sequence will be unknown to all other personnel, including study coordinators, outcome assessors and investigators.

Randomised allocation will be revealed to the participant by phone or email, which will provide detail of the allocated intervention. If they have been allocated to SWiM, they will receive a web link to access the website with instructions for getting started. If allocated to standard advice waitlist control, they will be emailed a PDF of the European Association for the Study of Obesity (EASO) guidance on diet, physical activity and mood during the COVID 19 pandemic.(6)

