6. OUTCOMES AND MEASURES

6.1 Primary Outcome

Self-reported weight at 4 months.

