8. STATISTICS AND QUANTITATIVE DATA ANALYSIS

8.1 Statistical analysis

A detailed statistical analysis plan will be developed and signed off by the Trial Steering Committee (TSC) prior to analysis. Participants will be analysed in the group to which they were randomised, based on the intention-to-treat principle. The primary analysis will estimate the baseline-adjusted difference between intervention groups in change in weight from baseline to 4 months, using a linear regression model including randomisation group, baseline weight, and the randomisation stratifiers (sex, BMI classification). Participants with missing values of weight at 4 months will be excluded (ie, a complete-case analysis which assumes outcome data are missing at random conditional on covariates in the model). If there are >5% of participants with missing values of weight, a sensitivity analysis will be performed using multiple imputation by chained equations – this makes the missing at random assumption but provides increased precision compared with a complete-case analysis. Linear regression will be used to estimate the baseline-adjusted difference between intervention groups in change in weight from baseline to 12 months and 4 months to 12 months. Since the control group was waitlisted and therefore received access to the SWiM website after the 4-month follow-up, analyses at 12 months will need to account for intervention usage in the control group. Regression models for the 12-month follow-up will therefore include intervention engagement (as measured using the intervention engagement questionnaire and/or website analytics) as a covariate. Full details of this analysis will be provided in the statistical analysis plan. Continuous secondary outcomes will be analysed using the same method.

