# 1 Introduction

### 1.1 Trial background and rationale

The social distancing and isolation measures imposed during the COVID-19 pandemic beginning March 2020, including the closure or reduced operating of some weight management programmes and services, mean that adults with overweight and obesity in the UK are at increasing vulnerability to weight gain, and associated negative impacts on physical health and mental wellbeing. There is good evidence that interventions based on acceptance and commitment therapy (ACT) are effective for weight management and may improve mental wellbeing and psychological determinants of weight control.(4) However, acceptance-based programmes are usually psychologist-led and the cost and scarcity of psychologists specialising in obesity mean it is not possible to support everyone who would benefit from this type of intervention.

We developed a supported self-help intervention (SWiM-C; Supporting Weight Management during COVID 19) that aims to help adults with overweight and obesity to manage their weight and eating behaviour, be more physically active, and protect their emotional wellbeing during the COVID pandemic. The 12-week intervention is based on ACT, targets known psychological determinants of weight management and is delivered via an online platform with remote support from a guide or coach.

If the SWiM-C intervention proves to be effective it could be rolled out on a larger scale to support people in situations involving high levels of stress, reduced access to resources, and/or low levels of mobility.

We previously evaluated the effect of SWiM-C on bodyweight in adults with overweight and obesity at 4 months post intervention compared to standard advice (written materials giving advice on diet, physical activity and mental health during the COVID-19 pandemic). The data were compatible with no effect of the intervention on bodyweight, physical activity, mental health, or emotional eating. The intervention improved psychological determinants known to lead to successful weight management in the longer term (uncontrolled eating, cognitive restraint, and experiential avoidance) and had a protective effect on wellbeing.

The current study compares the effectiveness of SWiM-C with standard advice at 12 months post intervention.

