### Secondary objectives:

- To evaluate the effect of SWiM-C over 12 months on eating behaviour, physical activity, health-related quality of life, capability and wellbeing, depression, anxiety, perceived stress, and experiential avoidance/psychological flexibility, compared to standard advice.
- To evaluate the effect of SWiM-C on change in weight from 4 months to 12 months, compared to standard advice

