### **Primary outcome**

The mean and SD of weight at baseline, 4-month and 12-month follow-up will be presented, together with the mean and SD of weight change from baseline to 4 months, 4 months to 12 months, and baseline to 12 months, separately in each randomised group.

The intervention effect on weight at 12 months (and 95% CI) will be estimated from a random intercepts linear regression model, using measures of change in weight at 4 months and 12 months as outcomes. The model will include intervention group, assessment timepoint, intervention by assessment timepoint interaction, the randomisation stratifiers (sex, BMI classification), and baseline value of weight as fixed effects, and random intercepts to allow for the repeated measures on each individual:

(Change in weight from baseline to timepoint t)i =  $\beta_0 + u_i + \beta_1 x$  groupi +  $\beta_2 x$  (t=4)i +  $\beta_{12} x$  (t=4)i\*groupi +  $\beta_3 x$  baselineweighti + randomisation stratifiers +  $\varepsilon_{it}$ 

*i*=individual, t=4 or 12 months (follow-up timepoint). (*t=4*)*i* = 1 if timepoint=4 months, 0 otherwise. *u**i* has a normal distribution with mean 0, variance  $\sigma_u^2$  and represents the (level 2) between-individual error. *ɛ**i*t has a normal distribution with mean 0, variance  $\sigma^2$  and represents the overall (level 1) residual error.

Then  $B_1$  represents the baseline-adjusted difference in weight change at 12 months comparing intervention vs control.

NOTE:  $\mathbf{6}_1 + \mathbf{6}_{12}$  represents the baseline-adjusted difference in weight change at 4 months comparing intervention vs control – not of interest in this analysis since it has previously been reported.

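### The model for weight change from 4 to 12 months adjusts for 4-month weight, a post-randomisation outcome, so it does not estimate the baseline-adjusted difference in change that the SAP promises

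*SAP*

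**What the plan says.** SAP section 1.2 lists as a secondary objective: "To evaluate the effect of SWiM-C on change in weight from 4 months to 12 months, compared to standard advice". Under Secondary outcomes in section 5.2 the SAP states the target: "We will estimate baseline-adjusted differences between the study groups in change in weight from 4 months to 12 months". The model given for it is a linear regression with "change in weight from 4 months to 12 months as the outcome, and including baseline weight, 4 month weight, the randomisation stratifiers" and intervention group.

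Protocol section 8.1 plans the same analysis as a "baseline-adjusted difference between intervention groups in change in weight from baseline to 12 months and 4 months to 12 months", and does not name 4-month weight as a covariate. SAP section 5.5, on protocol deviations, explains only the move to a random intercepts model. Neither document gives a reason for adding 4-month weight.

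Three other places bear on the point:

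- Protocol section 4.2 places randomisation at the start: "Once baseline data have been collected, eligible participants will be allocated to one of the two intervention arms in a 1:1 allocation". Nobody is randomised again at 4 months.
- Protocol section 6.1 names the primary outcome as "Self-reported weight at 4 months".
- SAP section 1.1 says of the 4-month results: "The data were compatible with no effect of the intervention on bodyweight, physical activity, mental health, or emotional eating". It gives no estimate or interval.

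**The concern.** Adjusting a change score for its starting value is harmless when that value was recorded before randomisation. Here it was recorded after about four months of SWiM-C or standard advice, so the intervention may have altered it. Holding it fixed removes part of the randomised effect. It also compares people who arrived at the same 4-month weight by different routes, and randomisation does not protect that comparison.

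The analysis exists to show whether any early difference is kept, lost or extended after month 4. If an early benefit were simply maintained, the model would credit SWiM-C with some further benefit. If it were fully regained, the model would understate the regain. The result would also disagree with the difference between the 12-month and 4-month effects.

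**Working it through.** **Inputs from the documents.** Protocol section 8.2: SD of weight 6 kg, correlation between repeated measures 0.9, difference of 1 kg, 90% power, 5% level (taken as two-sided), 20% dropout, 360 participants. SAP section 2.5: 388 recruited (192 and 196).

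**Reproducing the plan's figure.** Neither document gives a figure for the 4-to-12-month model, so the inputs were checked against the sample size.
- Baseline-adjusted SD = 6 × √(1 − 0.9²) = 2.615 kg.
- This needs 144 per group, and 144 / 0.8 = 180 per group, or 360 in total. That matches the protocol.
- The change-score SD, 6 × √(2 × 0.1) = 2.683 kg, would need 152 per group and 380 in total, which does not match.

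**What the coefficient estimates.** Let τ4 and τ12 be the randomised effects on weight at 4 and 12 months, and b4 the slope of 12-month on 4-month weight given baseline.
- Target (difference in change): τ12 − τ4
- Group coefficient with 4-month weight in the model: τ12 − b4 × τ4
- Gap (coefficient minus target): (1 − b4) × τ4

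The gap does not shrink with sample size. For participants with both weights, the same identity holds exactly between the fitted coefficients, so it is the observed 4-month difference that sets the gap in the report.

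**Size of b4.** With equal SDs, b4 = (r4,12 − r0,12 × r0,4) / (1 − r0,4²). The documents give only 0.9, so the correlations involving 12-month weight are assumptions:

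| r0,4 | r4,12 | r0,12 | b4 | Gap per 1 kg of τ4 |
|---|---|---|---|---|
| 0.90 | 0.90 | 0.90 | 0.47 | 0.53 kg |
| 0.90 | 0.85 | 0.80 | 0.68 | 0.32 kg |
| 0.90 | 0.90 | 0.85 | 0.71 | 0.29 kg |
| 0.90 | 0.90 | 0.81 | 0.90 | 0.10 kg |

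For the first row, (0.9 − 0.81) / 0.19 = 0.474.

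**Simulation** (144 per group, 2,000 replicates, all correlations 0.9):
- A 1 kg benefit at 4 months exactly maintained at 12: the true difference in change is 0. The SAP model averages −0.52 kg; the model without 4-month weight averages 0.01 kg.
- A 1 kg benefit fully regained: the truth is +1.0 kg. The SAP model averages +0.47 kg; without 4-month weight, +1.00 kg.

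These runs confirm the algebra. They are not a forecast for this trial.

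**A plausible τ4 here.** Reading SAP section 1.1 as a non-significant 4-month difference (an assumption), the largest such estimate on planning inputs is:
- 1.96 × 2.615 × √(2/144) = 0.60 kg with 144 per group
- 1.96 × 2.615 × √(1/192 + 1/196) = 0.52 kg with all 388 observed

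The gap is then at most 0.10 × 0.52 = 0.05 kg under the most favourable correlations and 0.53 × 0.60 = 0.32 kg under the least favourable.

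**Precision.** With 144 per group and τ4 = 0, removing 4-month weight moves the standard error from 0.27 to 0.32 kg (about 17%) if all correlations are 0.9, and from 0.308 to 0.310 kg if r0,12 is 0.81. The two middle rows of the table give 3 to 4%.

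**The case against.** The strongest reply is that the practical effect is small. The gap vanishes if τ4 is zero, and SAP section 1.1 points towards a small τ4 in a trial sized for 1 kg that recruited more than planned. SAP section 3.1 treats all secondary outcomes as exploratory and reports no p-value for them. Section 5.2 also tabulates mean 4-to-12-month change by group, so the raw difference will be visible. All of this stands and limits the size of the point. It does not make the model estimate its stated target, because data compatible with no effect do not show that τ4 is zero.

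A second reply is that adjusting for an interval's starting value is conventional, and that a comparison at equal 4-month weight is a coherent question. It is coherent, but it is a different question from the one in SAP section 1.2. Nor can 4-month weight be what the SAP means by baseline, since baseline weight is a separate covariate in the same model.

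A third reply is that the covariate improves precision. With all correlations at 0.9 it does, but the smaller error then belongs to a different quantity.

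A reader might infer that the trial will report a false continuing benefit or a false rebound of several tenths of a kilogram. That requires a 4-month effect near the 1 kg design value, which the reported 4-month result does not support.

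**Conclusion.** The point holds as a mismatch between a stated target and its model. The 4-to-12-month regression estimates τ12 − b4 × τ4, not the baseline-adjusted difference in change that the SAP and protocol section 8.1 ask for, and nothing elsewhere in the documents justifies or corrects this.

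The gap is 0.10 to 0.53 kg per 1 kg of 4-month effect. For this trial it is probably at most about 0.05 to 0.3 kg, depending on the correlations, and zero if τ4 is zero. These figures rest on the protocol's SD and correlation, equal SDs at each visit, assumed correlations with 12-month weight, and a non-significant 4-month difference.

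A reader might also infer that the main 12-month result is compromised. It is not: the primary model does not condition on 4-month weight as a covariate, and its group coefficient "represents the baseline-adjusted difference in weight change at 12 months comparing intervention vs control".

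**What to change.** Delete 4-month weight from the covariates of the 4-to-12-month regression, and keep baseline weight, the stratifiers and group. The model then estimates the difference that the SAP names.

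Alternatively, report −β12 with its 95% CI from the primary repeated-measures model, since β1 − (β1 + β12) = −β12. That model first needs a baseline-weight-by-timepoint term. Without one, and with complete data, −β12 is simply the unadjusted difference in mean change. To reproduce the regression exactly with complete data, the stratifiers need timepoint terms as well.

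If the comparison at equal 4-month weight is wanted, keep it as a supplementary analysis, labelled as conditional on a post-randomisation value.

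The cost is a short wording change. The standard error rises by about 0 to 4% under most of the correlations examined. If all correlations are 0.9 it rises by about 14 to 17% by calculation, and by up to 19% in simulation.

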#### **Testing assumptions**

Prior to analyses, we will assess the assumptions underlying linear regression.

### Linear regression

*Normality of residuals*: Normality will be assessed by visually inspecting the frequency distribution of the standardised residuals (for both within and between person error). Variables with a skewed distribution will be log-transformed and then re-checked for violations of normality. Violations of normality should not affect the validity of the method as our sample size will be large (7).

*Heteroscedasticity*: Heteroscedasticity will be explored by visually examining the regression plot plotting the standardized residuals of the outcome against the standardized predicted values of the model.

### **Missing data**

We will conduct analyses with all observed data; random intercept models use all available data and assume missing data are missing at random. To explore this assumption, we will descriptively compare participants with and without missing outcome data on baseline characteristics.

### 5.3 Safety data

This is a low-risk trial with little reason to consider that adverse events would arise as a result of following any one of the interventions. Accordingly no formal adverse event monitoring is planned (12).

### 5.4 Statistical software

Data will be analysed using R version 4.1.2 (unless newer versions become available in the interim) and R Studio version 1.4. Where required data will also be analysed using Stata version 16.1.

### 5.5. Protocol deviations

The SWiM-C protocol states that we will do a linear regression analysis with change from baseline as the outcome. This protocol was written when only one follow-up assessment at 4 months was planned, before we had decided to include the 12-month follow-up. As we now have two follow-up timepoints, we have opted for a random intercepts model to allow for the repeated measures on each individual.

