2. AIMS AND OBJECTIVES

2.1 Aim

To evaluate the effect of the SWiM intervention on weight, eating behaviour, physical activity and wellbeing compared to current standard advice for people with overweight and obesity. Primary Objective

To evaluate the effect of SWiM on weight at 4 months and 12 months follow-up, compared to standard advice on diet, physical activity and mood.

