3. STUDY DESIGN

This is a pragmatic, randomised, single-blind, parallel group, two-arm trial. Participants will be randomised to either the SWiM intervention or to a standard advice wait list control using a computer-generated sequence with 1:1 allocation stratified by sex and BMI classification.

Participants will complete outcome assessments online at baseline, at 4 months and at 12 months follow-up.

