7. MEASUREMENTS AND DATA COLLECTION

7.1 Visit Schedule

Participants will complete online assessments at 0,4 and 12 months. Details of which measures will be taken at each time point are summarised in Table 4. Participants will be given an honorarium for completing (£10 for baseline and £20 for the 4 and 12 month visit). Honoraria for assessment completion are not dependent on intervention engagement/completion.

TABLE 4: Schedule of Enrolment, Interventions, and Assessments

| | STUDY PERIOD | | | |
|------------------|-----------------|----------|-----------|-----------|
| | Enrolment | Baseline | Follow Up | |
| TIMEPOINT** | -t ₁ | 0 | 4 months | 12 months |
| ENROLMENT: | | | | |
| Online screening | X | | | |

| | | | | |
|--------------------------------------|--|--|---|---|
| Informed consent | | X | | |
| Randomisation | | X | | |
| INTERVENTIONS: | | | | |
| Supporting Weight Maintenance (SWiM) | |  | | |
| Standard Advice | | X | | |
| ASSESSMENTS: | | | | |
| Height | | X | | |
| Weight | | X | X | X |
| Demographics | | X | | |
| Eating Behaviour | | X | X | X |
| Physical Activity | | X | X | X |
| Quality of Life /Wellbeing | | X | X | X |
| Intervention Engagement | | | X | X |

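### SAP 5.5 explains the change of 12-month model by a protocol without a 12-month visit; the supplied protocol has one and names linear regression for it, and no such regression from baseline to 12 months is kept as a check.

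*SAP*

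**What the plan says.** SAP 5.5 records one deviation, the change of model. Its reason is "This protocol was written when only one follow-up assessment at 4 months was planned, before we had decided to include the 12-month follow-up", followed by "As we now have two follow-up timepoints, we have opted for a random intercepts model to allow for the repeated measures on each individual".

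The supplied protocol plans the 12-month visit in several places:
- Section 2.1, under the primary objective heading: "To evaluate the effect of SWiM on weight at 4 months and 12 months follow-up, compared to standard advice on diet, physical activity and mood".
- Section 3: "Participants will complete outcome assessments online at baseline, at 4 months and at 12 months follow-up".
- Section 7.1: "Participants will complete online assessments at 0,4 and 12 months". Table 4 and section 7.2 agree.
- Section 8.1: "Linear regression will be used to estimate the baseline-adjusted difference between intervention groups in change in weight from baseline to 12 months". The same sentence covers the change from 4 to 12 months. The section adds intervention engagement as a covariate in the 12-month models and leaves full details to the SAP.

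SAP 3.1 and 5.1 make weight change from baseline to 12 months the single primary endpoint. For it, SAP 5.2 says: "The intervention effect on weight at 12 months (and 95% CI) will be estimated from a random intercepts linear regression model". That model has one between-person variance and one residual variance, and no engagement term. SAP 5.2 keeps ordinary linear regression for the 4-to-12-month change, and handles engagement through two per-protocol subsets.

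**The concern.** The reason recorded for changing the confirmatory model does not fit the protocol supplied with the SAP. There, linear regression at 12 months was named with both follow-ups in view. Nor does a second follow-up require a repeated-measures model: the confirmatory endpoint is one value per person, and the SAP still uses ordinary regression for the 4-to-12-month change.

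Timing adds weight. The SAP versions run from January to March 2022, and SAP 1.1 already reports the 4-month comparison. A change of confirmatory model at that stage needs an accurate record and a check that the answer does not depend on it. The SAP plans no second estimate of the baseline-to-12-month effect in the full randomised groups. Two further departures go unlisted in 5.5: the engagement covariate is dropped, and the primary endpoint moves from 4 months (Protocol 6.1) to 12 months.

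**Working it through.** **1. The plan's own figure.** Protocol 8.2 gives a 1 kg difference at 4 months, SD 6 kg, correlation 0.9, 90% power, 5% level (taken as two-sided) and 20% dropout. The baseline-adjusted SD is 6 × √(1 − 0.9²) = 2.615 kg. Then n per arm = 2 × (1.96 + 1.2816)² × 2.615² / 1² = 143.7, so 144. Dividing by 0.8 gives 180 per arm, or 360, which matches. The calculation thus rests on a baseline-adjusted comparison at 4 months. The documents give no SD of weight change at 12 months, so the SD ratios below are assumptions.

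**2. What the SAP model assumes.** With a random intercept variance σ_u² and a single residual variance σ², the variance of weight change is σ_u² + σ² at both visits. Let the true SDs be s₄ and s₁₂, with ratio k = s₁₂/s₄. With complete data the fitted common variance is close to the average, (s₄² + s₁₂²)/2. The 12-month group coefficient is almost the same as from a 12-month regression, so its true variance depends on s₁₂² alone. Hence

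model SE / true SE = √[(1 + 1/k²)/2] = f, and true type I error = 2 × [1 − Φ(1.96 × f)].

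| k | 1/k² | f | 1.96 × f | True type I error |
|---|---|---|---|---|
| 1 | 1 | 1 | 1.960 | 5.0% |
| 1.33 | 0.565 | 0.885 | 1.734 | 8.3% |
| 1.5 | 0.444 | 0.850 | 1.666 | 9.6% |
| 2 | 0.250 | 0.791 | 1.550 | 12.1% |

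A regression on 12-month data alone estimates s₁₂ directly and keeps about 5%.

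**3. Simulation check.** Each row has 388 participants (192 and 196, SAP 2.5) and 300 runs, with a true 12-month effect of −1 kg. The within-person correlation of 0.6, the SDs and the missingness (completely at random) are assumptions.

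| SD at 4 / 12 months (kg) | Missing at 4 / 12 months | SAP model: model SE, empirical SD, 95% CI coverage | 12-month regression: same | Mean absolute gap between estimates |
|---|---|---|---|---|
| 2.615 / 2.615 | 0 / 0 | 0.265, 0.264, 95.0% | 0.265, 0.264, 95.0% | 0.004 kg |
| 2.615 / 2.615 | 15% / 25% | 0.295, 0.267, 96.3% | 0.307, 0.278, 97.0% | 0.070 kg |
| 2.615 / 5.2 | 15% / 25% | 0.460, 0.601, 85.3% | 0.611, 0.625, 94.0% | 0.056 kg |

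A separate null simulation at k = 1.5 (388 participants, 300 runs) rejected in 9.3% of trials with the SAP model and 5.0% with the regression. One model was significant and the other not in 4.3%. With 300 runs, the Monte Carlo standard error of the 9.3% is √(0.093 × 0.907 / 300) = 1.7 percentage points, so it agrees with the 9.6% from the formula.

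**4. Reading.** The change of model barely moves the estimate. What it can change is the stated uncertainty, and only if the spread of weight change differs between visits. If the spread grows, the test is too liberal; if it shrinks, f exceeds 1 and the test is conservative.

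**The case against.** A reader might infer that the reason in 5.5 is simply untrue. The documents do not establish that. The supplied protocol reads as a revised text: sections 7.2 and 8.1 say in the past tense that controls were given the website after month 4, while section 5.2 still promises access once the study is over. The primary outcome (6.1) and sample size (8.2) cover 4 months only. All this fits an earlier version with one follow-up. Title pages are not in the supplied text, so a missing version number there is no fault. What stands is that 5.5 does not describe the protocol version supplied.

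A reader might also infer that the pre-specified analysis is lost, or that the change is passed off as forced. Neither goes that far. The 4-to-12-month regression is kept, and the new model targets the same baseline-adjusted 12-month difference with the same stratifiers. The protocol left details to the SAP, and 5.5 openly lists the change as a choice.

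Nor do the documents show that the 4-month result drove the choice of model. They show only the order of events.

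The model has real merits. It uses 4-month data from people missing at 12 months, and with equal SDs it is slightly more precise (SE 0.295 against 0.307 above).

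The protocol's own 12-month model includes engagement, so a regression without it is not that model. Engagement is measured after randomisation, and adjusting for it would not estimate the intention-to-treat effect, so leaving it out is defensible. The departure still needs recording.

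Lastly, SAP 5.2 will report the SD of weight change for each interval and plans a residual plot for heteroscedasticity. Unequal spread could therefore be noticed. But no remedy is stated, and no planned estimate would show whether the conclusion changes.

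**Conclusion.** The point holds in a limited form. SAP 5.5 conflicts with the supplied protocol, which plans the 12-month visit and names linear regression with an engagement covariate for change from baseline to 12 months. The SAP replaces that regression for its confirmatory endpoint after the 4-month result was known, and keeps no baseline-to-12-month regression as a check.

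Correcting the record alone alters no result. The added analysis is worthwhile because the planned model's type I error is about 8%, 10% or 12% if the 12-month SD is 1.33, 1.5 or 2 times the 4-month SD, with complete data. These ratios are assumptions, since the documents give no 12-month SD. If the SDs are equal, the two analyses nearly agree and the change of model is harmless. This is a change the plan should make, and the planned model is otherwise a reasonable choice.

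**What to change.** 1. Add to SAP 5.2, as a named sensitivity analysis reported beside the primary estimate whatever it shows, the linear regression of weight change from baseline to 12 months on group, baseline weight, sex and BMI class. Alternatively, allow visit-specific residual variances in the planned model.
2. Correct SAP 5.5 so that it:
   - cites the protocol version it refers to;
   - acknowledges that section 8.1 of the current protocol names a 12-month linear regression with an engagement covariate;
   - states that the model was chosen after the 4-month results were known;
   - records the dropped engagement covariate, with the reason, and the move of the primary endpoint from 4 to 12 months.

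The investigators should give their own reason for preferring the random intercepts model.

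The cost is a rewritten section and one extra regression. The downside is a second 12-month estimate in the report, which is manageable if one is named in advance as confirmatory.
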